10.0 Data Safety Monitoring

A data safety monitoring board (DSMB) composed of [name] (FPMRS faculty), [name] (FPMRS faculty), [name] (FPMRS faculty) and [name] (FPMRS fellow) will be scheduled to meet every 6 months and review the data for patient safety. This will be monitored as part of the Data Safety Monitoring Plan (DSMP): data quality, subject recruitment, accrual, retention, outcome and adverse event data, assessment of scientific reports or therapeutic development, results of related studies that may impact subject safety, and procedures designed to protect the privacy of subjects.

The purpose of this committee will be to evaluate logistical problems and determine if the study should be stopped. Examples of logistical problems would include enrollment rates, follow up rates, or dropout rates. Reasons to stop the study would include if the objective is met prematurely, if the study gives sufficient data against the premise, if the study is proven to be futile, or if there is high index of suspicion that the intervention is harmful. The DSMB will also advise about study progress and performance, protocol changes, and if additional monitoring is necessary.

Version Date: 05/25/2023 Page 9 of 13

11.0 Study Withdrawal/Discontinuation

Participants will be withdrawn from the study if they refuse to answer the NRS at the approximate 4 hour mark. Participants may elect to discontinue their involvement in the study at any time. In events of participant withdrawal, we will assess if they would like complete withdrawal of all data or up to that point of their involvement.

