3.0 Outcome Measures/Endpoints

- 3.1 Primary Outcome Measures
- 3.2 Secondary Outcome Measures
- 3.1: Patient pain will be measured by means of a NRS at 4 hours after surgical pelvic organ prolapse repair.
- 3.2: Patient pain will be measured by means of a NRS at 8, 12 and 24 hours after surgical pelvic organ prolapse repair. Total opiate consumption will be measured in MME, obtained from the electronic medical record. Time to first narcotic dose will be measured in hours and minutes. Hospital length of stay will be measured in days, hours and minutes.

Patients receiving an opioid prescription after short stay surgeries have a 44% increased risk of long term opioid use. The first 4-24 hours postoperatively is the time when these prescriptions are provided. With appropriate control of postoperative pain in the first 4-24 hours, patients may be able to be discharge without opiate prescription.

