7.0 Study Procedures

In the study, patients will be randomized to one of two groups. Arm 1 will be participants who receive intraperitoneal bupivacaine and arm 2 will be participants who receive placebo (saline).

All patients involved in the study will be undergoing pelvic organ prolapse surgery with peritoneal access and will receive either 30 mL of 0.25% Bupivacaine or 30 mL of saline by means of intraperitoneal lavage. This will be performed at which point peritoneal access will no longer be available, and the solution will be left in the abdomen upon completion of the procedure.

Preoperatively, patients will receive a standardized pain control regimen of Ibuprofen and Tylenol in accordance with hospital ERAS protocol. Postoperatively, patients will receive standardized pain control regimen of Ibuprofen and Tylenol in accordance with hospital ERAS protocol. Patients can be given as needed narcotics if pain is poorly controlled on the initial regimen.

All patients will have pain scores measured at approximately 4 hours using a NRS following completion of the procedure. All patient will have pain scores measured at approximately 8, 12 and 24 hours by means of text message NRS (in the event of same day surgery discharge) vs inpatient in person NRS (for planned admission), following completion of the procedure, which will be stored directly into REDCap. Time to first narcotic dose will be obtained through the hospital electronic medical record. Hospital length of stay will be obtained through the hospital electronic medical record.

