Assuming baseline characteristics are balanced between the two study arms, we will use a linear mixed model fit to all timepoints (4, 8, 12, and 24 hours) with effects of surgery technique, treatment group, time, and the time x treatment group interaction to estimate the mean difference in treatment groups at each time point. All model assumptions will be checked for adequacy. The mean difference and 95% confidence interval at each time point will be reported. A p-value of 0.017 will be used to indicate statistical significance in the NRS collected at the three other time points (8, 12, and 24) to maintain familywise type I error at .05. For

Version Date: 05/25/2023 Page 10 of 13

the dichotomous outcome of whether patients required opioids in the first 4 hours following surgery, a Fisher's exact test will be used.

Other outcomes can only be assessed among those that required opioids thus will have lower power. Thus, caution will be used in interpretation of results. These include the amount of MME in the first four hours and time to first dose. Descriptive statistics by study group will be estimated. For outcomes which may be normal, then a linear regression model will be fit with effect of surgery technique and treatment, to estimate the mean difference in the outcome by treatment and associated 95% confidence interval. If any outcome is non-normal, then a generalized linear regression model will be used instead with an appropriate distribution and link function to detect the effect of treatment.

- 1. Cohen J. Statistical power analysis for the behavioral sciences. L. Erlbaum Associates; 1988.

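### Withdrawing participants who refuse the 4-hour pain score is an avoidable post-randomisation exclusion that also costs their 8, 12 and 24 hour scores

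*Combined protocol and SAP*

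**What the plan says.** Section 11.0 contains three separate provisions.

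- Withdrawal imposed by the study: "Participants will be withdrawn from the study if they refuse to answer the NRS at the approximate 4 hour mark".
- The participant's own right to leave: "Participants may elect to discontinue their involvement in the study at any time".
- What happens to the data on withdrawal: "we will assess if they would like complete withdrawal of all data or up to that point of their involvement".

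Section 7.0 sets the timing. The lavage is given during surgery. The first pain score follows ("All patients will have pain scores measured at approximately 4 hours using a NRS following completion of the procedure"), and later scores are taken by text message after same-day discharge or in person for planned admissions ("All patient will have pain scores measured at approximately 8, 12 and 24 hours by means of text message NRS"). The calendar in Section 8.0 shows no earlier pain score.

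Section 12.0 plans a "linear mixed model fit to all timepoints (4, 8, 12, and 24 hours"), with surgery technique, treatment, time and the time-by-treatment interaction. It sets N = 90 on the expectation of no attrition and no missing primary data. No section defines an analysis set or a missing-data method.

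**The concern.** The first provision in Section 11.0 stands apart from the participant's right to discontinue. It therefore reaches someone who declined one question but is willing to continue. That person has been randomised and treated, and refusal is a post-randomisation event that may depend on pain, which is the outcome.

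The rule also works against the planned analysis. A likelihood-based mixed model accepts a participant whose 4-hour value is missing and uses the later values. Under the rule those values would mostly never be collected, and neither data option in Section 11.0 covers them. A refuser therefore drops out of the randomised comparison at all four time points instead of one.

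Record-based outcomes may be affected too, but this is an inference. Section 3.0 says "Total opiate consumption will be measured in MME, obtained from the electronic medical record" and Section 7.0 says "Time to first narcotic dose will be obtained through the hospital electronic medical record". No sentence says chart extraction stops at withdrawal, and it is unclear whether the choice over data applies when the study imposes the withdrawal. Opioid data from the first 4 hours precede the rule and can be kept if the participant agrees. Total inpatient opioid use and length of stay have no named analysis in Section 12.0. The main losses are therefore the 8, 12 and 24 hour scores and, by inference, first narcotic doses after 4 hours.

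**Working it through.** **The plan's own figure.** Section 12.0 uses a difference of 1.3, an SD of 2.14 (the divisor in its effect-size calculation), an effect size of 0.60, two-sided alpha 0.05 and 80% power. A two-sample t-test at 0.60 needs 44.59 per arm, rounded up to 45, so N = 90 reproduces. Power at 45 per arm is 80.4%. The standard error of the difference is 2.14 × √(2/45) = 0.451.

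**Scores lost.** With refusal rate r (assumed) and three later scores each, the loss is up to 90 × r × 3.

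- 2%: 90 × 0.02 × 3 = 5.4
- 5%: 90 × 0.05 × 3 = 13.5
- 10%: 90 × 0.10 × 3 = 27

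**Bias: assumptions.** The documents supply only the SD and the target difference. The rest is assumed:

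- scores at the four times are normal with SD 2.14 and equal correlation 0.5 or 0.7;
- the true difference is 1.30 at every time;
- refusal follows a logistic curve in the 4-hour score, with log-odds slope 1 or 2 per SD (odds ratio 2.7 or 7.4);
- the curve is the same in both arms, with its intercept set to give 2%, 5% or 10% refusal on average.

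Three cases were simulated with 1.5 million patients per arm. In the first, refusers are withdrawn and give no scores. In the other two they are kept, and either a random half or all of them answer every later score. When they are kept, the 4-hour mean is adjusted by regression on the later scores, as a likelihood model does.

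**Estimated 4-hour difference (true value 1.30)**

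| Refusal | Slope | Correlation | Withdrawn | Kept, half answer | Kept, all answer |
|---|---|---|---|---|---|
| 2% | 1 | 0.5 | 1.275 | 1.279 | 1.283 |
| 2% | 1 | 0.7 | 1.276 | 1.284 | 1.290 |
| 2% | 2 | 0.5 | 1.238 | 1.249 | 1.260 |
| 2% | 2 | 0.7 | 1.236 | 1.255 | 1.273 |
| 5% | 1 | 0.5 | 1.248 | 1.258 | 1.267 |
| 5% | 1 | 0.7 | 1.249 | 1.265 | 1.280 |
| 5% | 2 | 0.5 | 1.175 | 1.198 | 1.219 |
| 5% | 2 | 0.7 | 1.174 | 1.212 | 1.248 |
| 10% | 1 | 0.5 | 1.211 | 1.228 | 1.242 |
| 10% | 1 | 0.7 | 1.208 | 1.237 | 1.260 |
| 10% | 2 | 0.5 | 1.096 | 1.134 | 1.164 |
| 10% | 2 | 0.7 | 1.098 | 1.162 | 1.213 |

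The largest gain from keeping refusers is 1.213 − 1.098 = 0.115 (0.115/0.451 = 0.26 standard errors) if all answer later, and 1.162 − 1.098 = 0.064 (0.14 standard errors) if half do.

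**Estimated 8-hour difference (true value 1.30), range over slopes and correlations**

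| Refusal | Withdrawn | Kept, half answer | Kept, all answer |
|---|---|---|---|
| 2% | 1.28 to 1.26 | 1.29 to 1.28 | about 1.30 |
| 5% | 1.27 to 1.21 | 1.29 to 1.26 | about 1.30 |
| 10% | 1.26 to 1.15 | 1.28 to 1.23 | about 1.30 |

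**No true effect.** At 4 hours, with 2% and 10% refusal, every estimate lay within 0.005 of zero (Monte Carlo error about 0.0025).

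**Precision alone.** At 8 hours, with the plan's threshold of 0.017 and an assumed effect size of 0.60, power is 66.0% with 45 per arm. It is 63.3% if 5% are lost (42.75 per arm) and 60.4% if 10% are lost (40.5 per arm).

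**The case against.** The strongest reply is that nothing in the documents shows the rule will matter. Section 12.0 expects no missing primary data, no refusal rate is given, and no passage links refusal to pain. If nobody refuses, the rule does nothing; if refusal is unrelated to pain, only a little precision is lost. This stands, and it is why the point is minor.

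A second reply is that most of the 4-hour bias comes from the refusal itself, which no wording can undo. This also stands. At 10% refusal and slope 2 the bias under the rule is about 0.20. With full later response, 1.300 − 1.164 = 0.136 or 1.300 − 1.213 = 0.087 remains (correlation 0.5 or 0.7), roughly 67% or 43% of it. With half responding, 0.166 or 0.138 remains, roughly 81% or 68%. The change mainly protects the later, secondary scores.

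Third, someone who actively refuses the first score may refuse the others, so full later response is a ceiling. That is fair, and the half-response figures are given for that reason.

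Finally, the null result holds only when refusal works the same way in both arms. With an assumed 10% refusal in one arm and 5% in the other, and no true effect, the 4-hour scores alone show a spurious difference of 0.09 to 0.14.

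None of this supplies a reason for the rule. If refusal is rare, keeping those participants costs almost nothing; if it is not rare, the rule does harm.

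**Conclusion.** The concern holds, as a minor point. That the rule is mandatory, separate from withdrawal of consent, and removes refusers from all four time points is clear from Sections 7.0, 11.0 and 12.0. How much it matters is not known from the documents. Under the assumed 2% to 10% pain-related refusal, common to both arms, the bias is toward no difference, and this model shows no false-positive risk. The part due to the rule is at most 0.12 points at 4 hours, about a quarter of a standard error. At 8 hours it is up to about 0.15 points (1.30 − 1.15) if all refusers would have answered later, and about 0.08 (1.23 − 1.15) if half would.

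**What to change.** In Section 11.0, replace the rule with: *A participant who refuses or misses the 4-hour NRS stays in the study; 8, 12 and 24 hour NRS and record-based outcomes are still collected unless the participant withdraws consent.* Naming missed scores as well removes any doubt about how they are handled.

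In Section 12.0, add: *All randomised participants with at least one NRS score enter the mixed model in their assigned arm.*

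A sensitivity analysis for missing 4-hour scores is optional. It would address the part of the 4-hour bias that continued follow-up cannot remove.

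The cost is two sentences and continued follow-up of a few participants: about 2, 4 to 5, or 9 of 90 at the assumed refusal rates. No extra enrolment is needed, and the participant's right to withdraw is unchanged.

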12.0 Statistical Considerations

Sample size/Power

This is a double-blind randomized controlled study to compare two techniques of pain management strategies for woman undergoing advance-organ prolapse surgery with the primary outcome being the numeric rate scale (NRS) at 4 hours post-surgery. Secondary outcomes will be the NRS collected at 8, 12, and 24 hours, and an indicator of whether woman required opioids (Y/N) within 4 hours of surgery.

Assuming a SD = 2.14^2 in the NRS at 4 hours, to detect a meaningful change of 1.3 would be an ES = 0.60 (1.3/2.14). To have 80% power to detect an effect size of this magnitude (i.e., a 0.6 SD difference in the NRS between treatment arms) based on a two-sided two-sample independent t-test with type I error set at 0.05 requires a total sample size of N = 90 (45 per group). As we expect no attrition or missing data on the primary outcome, N = 90 will be our planned sample size.

Randomization

Patients will be randomized 1:1 to the two pain strategies using stratified randomization with surgery technique being the strata. Block randomization will be used with blocks of size 4. Randomization lists will be constructed by the study statistician using statistical software.

Statistical Methods

Descriptive statistics of N, mean, standard deviation, median, minimum, and maximum or frequency and percent will be provided for all baseline characteristics overall and by treatment arm. Baseline characteristics which will be reported include surgical procedure (uterosacral ligament suspension vs sacrocolpopexy), age, BMI, menopausal status, surgical time, and intraoperative complications. Intraoperative complication will be a dichotomous variable of whether any complication occurred (Y/N). Baseline characteristics will be compared between the two study arms to verify randomization achieved balanced groups. Any characteristics that significantly differ will be considered in subsequent analyses.

Assuming baseline characteristics are balanced between the two study arms, we will use a linear mixed model fit to all timepoints (4, 8, 12, and 24 hours) with effects of surgery technique, treatment group, time, and the time x treatment group interaction to estimate the mean difference in treatment groups at each time point. All model assumptions will be checked for adequacy. The mean difference and 95% confidence interval at each time point will be reported. A p-value of 0.017 will be used to indicate statistical significance in the NRS collected at the three other time points (8, 12, and 24) to maintain familywise type I error at .05. For

Version Date: 05/25/2023 Page 10 of 13

the dichotomous outcome of whether patients required opioids in the first 4 hours following surgery, a Fisher's exact test will be used.

Other outcomes can only be assessed among those that required opioids thus will have lower power. Thus, caution will be used in interpretation of results. These include the amount of MME in the first four hours and time to first dose. Descriptive statistics by study group will be estimated. For outcomes which may be normal, then a linear regression model will be fit with effect of surgery technique and treatment, to estimate the mean difference in the outcome by treatment and associated 95% confidence interval. If any outcome is non-normal, then a generalized linear regression model will be used instead with an appropriate distribution and link function to detect the effect of treatment.

- 1. Cohen J. Statistical power analysis for the behavioral sciences. L. Erlbaum Associates; 1988.

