2.0 Objective(s)

- 2.1 Primary Objective
- 2.2 Secondary Objective

2.1: To determine whether intraperitoneal Bupivacaine will decrease pain scores at approximately 4 hours, as determined by a numeric rating scale (NRS) in patients undergoing pelvic organ prolapse repair.

Version Date: 05/25/2023 Page 5 of 13

2.2: Pain scores as determined by NRS at approximately 8, 12 and 24 hours, total opiate consumption postoperatively while inpatient as determined by morphine milligram equivalents (MME), time to first narcotic dose during inpatient stay, and hospital length of stay.

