5.0 Study Design

This will be a double blinded randomized controlled trial. This is the ideal study design as it will serve the purpose of measuring the effectiveness of an understudied intervention (intraperitoneal Bupivacaine) in the management of postoperative pain. Randomization and blinding will help to reduce bias and better assess cause-effect relationships between the intervention and outcome. This study will be done in conjunction with Investigational Drug Services (IDS), who will manage randomization and blinding according to their division protocols. Covariate to be collected include age, BMI, menopausal status, type of surgical procedure, surgical time, and intraoperative complications (Y/N).

Version Date: 05/25/2023 Page 7 of 13

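### A preoperative NRS, used as a prespecified covariate, would be a cheap gain in precision; the plan takes none, though its 4-hour comparison is valid without it

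*Combined protocol and SAP*

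**What the plan says.** Every planned pain score is postoperative. The primary objective (section 2.0) is "To determine whether intraperitoneal Bupivacaine will decrease pain scores at approximately 4 hours", and the endpoint (section 3.0) reads "Patient pain will be measured by means of a NRS at 4 hours after surgical pelvic organ prolapse repair". Section 7.0 sets the first measurement: "All patients will have pain scores measured at approximately 4 hours using a NRS following completion of the procedure". The later ones follow at 8, 12 and 24 hours. The calendar in section 8.0 shows consent at enrolment, the study solution at surgery, and NRS only at the four postoperative times.

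The covariate list in section 5.0 has no pain score: "Covariate to be collected include age, BMI, menopausal status, type of surgical procedure, surgical time, and intraoperative complications (Y/N". The baseline list in section 12.0 names the same six items: "Baseline characteristics which will be reported include surgical procedure (uterosacral ligament suspension vs sacrocolpopexy), age, BMI, menopausal status, surgical time, and intraoperative complications". The arms are to be compared on these, and "Any characteristics that significantly differ will be considered in subsequent analyses". The mixed model is specified "with effects of surgery technique, treatment group, time, and the time x treatment group interaction", with no term for preoperative pain.

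**The concern.** When an outcome is measured repeatedly on one scale, its pre-treatment value is a natural candidate covariate. Here it is never collected, so it can neither enter the model nor be described by arm.

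The plan's balance check also covers less than its list suggests. Surgical time and intraoperative complications arise during surgery, and surgical procedure is already balanced by stratification. That leaves age, BMI and menopausal status. Section 4.2 excludes chronic opiate users but not patients with existing pain managed without opioids, so preoperative pain is free to differ between patients, and by chance between arms. A score not taken before surgery cannot be recovered later unless routine records happen to hold one, and the plan does not say that any would be extracted.

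At stake are the width of the confidence interval for the primary difference and the ability to allow for an uneven start.

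**Working it through.** **Inputs.** From section 12.0: difference 1.3 points; SD 2.14 (the text prints a superscript 2 after it, but divides 1.3 by 2.14, so 2.14 is taken as the SD); two-sided alpha 0.05; 45 per arm. Assumed, because the documents do not give it: r, the correlation between preoperative and 4-hour NRS, from 0.1 to 0.5.

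**Step 1: the plan's own figure.** A two-sample t-test at effect size 0.60 with 80% power needs 44.59 per arm, hence 45 and N = 90. Power at 45 per arm is then 80.4%. With the unrounded effect size, 1.3/2.14 = 0.607, power is 81.3%. The stated sample size reproduces; 81.3% is the starting point below.

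**Step 2: effect of adjustment.**
- Residual SD = 2.14 × √(1 − r²).
- Adjusted effect size = 1.3 / residual SD, put into the same t-test power calculation.
- 95% CI half-width = 1.987 × residual SD × √(2/45), where 1.987 is the t quantile on 88 degrees of freedom and √(2/45) = 0.211.

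| r | Residual SD | Effect size | Power | CI half-width (points) |
|---|---|---|---|---|
| 0 (as planned) | 2.14 | 0.607 | 81.3% | 0.90 |
| 0.1 | 2.13 | 0.611 | 81.7% | 0.89 |
| 0.2 | 2.10 | 0.620 | 82.9% | 0.88 |
| 0.3 | 2.04 | 0.637 | 84.8% | 0.86 |
| 0.5 | 1.85 | 0.702 | 90.8% | 0.78 |

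In equivalent sample size, 90/(1 − r²), the adjusted analysis is worth about 99 unadjusted patients at r = 0.3 and 120 at r = 0.5.

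**Step 3: size of a chance imbalance.** The difference between arms in mean preoperative NRS has a standard error of √(2/45) = 0.21 SD, so its 95% range is about ±1.96 × 0.211 = ±0.41 SD. An imbalance at the edge of that range would move the unadjusted 4-hour difference by r × 2.14 × 0.413:
- r = 0.1: 0.09 points (7% of 1.3)
- r = 0.2: 0.18 points (14%)
- r = 0.3: 0.27 points (20%)
- r = 0.5: 0.44 points (34%)

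This is a near-worst chance draw, not an expected shift; the expected shift is zero.

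**Limits.** The calculation uses the plan's t-test setting, not the full mixed model. It ignores any variance already explained by surgery technique and the few degrees of freedom spent on the new terms.

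**The case against.** The strongest reply is that nothing is broken. The endpoint is the NRS at 4 hours, not a change from baseline. Allocation is randomised 1:1 within surgery technique, and technique is in the model. The comparison is therefore unbiased without a baseline, and its confidence interval already allows for chance differences in unmeasured variables, preoperative pain included. N = 90 meets the 80% target. All of this stands.

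A reader might infer that the missing baseline biases the primary result, or that the plan's balance check fails because it omits the variable most closely tied to the outcome. The documents support neither. Randomisation answers the first. On the second, nothing in the documents says how strongly preoperative pain predicts acute pain at 4 hours under a standardised ibuprofen and Tylenol regimen with narcotics as needed. Nor should a balance test decide whether to adjust, so its blind spot is weak evidence of harm.

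It also stands that the gain is modest over much of the assumed range: under 2 points of power at r of 0.2 or less, and 3.5 at 0.3. Only the top of the range is substantial. Nor does the existing consent contact supply the measurement for everyone. Section 6.0 allows consent at an earlier office visit, so a day-of-surgery score would be a new step for those patients.

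What the reply does not remove is that the gain is cheap and cannot be had afterwards from data never collected.

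**Conclusion.** The point holds as a low-cost improvement, not as a defect of validity. The plan records no NRS before surgery and so gives up some precision and the option to adjust for a chance imbalance. If r lies between 0.1 and 0.5, collecting it would add about 0.4 to 9.5 points of power to the planned 81.3% and shorten the CI half-width by about 0.01 to 0.12 points. These figures rest on SD 2.14, 45 analysed patients per arm and an r that the documents do not give. If preoperative scores cluster near zero, expect the low end.

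**What to change.** - **Collection:** record a 0-10 NRS for every patient at one common time, on the day of surgery, before randomisation and before the preoperative analgesics. Add it to the calendar in section 8.0, the covariates in section 5.0 and the baseline characteristics in section 12.0.
- **Analysis:** prespecify it in the section 12.0 mixed model as a covariate with its interaction with time, kept regardless of any balance test.

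**Cost.** One question and one REDCap field per patient, with an added step for those consented earlier at the office. The model gains up to four coefficients, since the covariate's slope may differ at each of the four times. Patients already enrolled would lack the value; mean imputation or a missing indicator would keep them in the analysis, and the gain shrinks as their number grows.

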Bupivacaine vs placebo in patients undergoing bariatric surgical procedures. In this study, 106 patients were assigned to receive intraperitoneal lavage with 50 mL of 0.2% Bupivacaine or the same volume of normal saline during the procedure. Using a VAS, patients postoperative pain was rated at 1, 4, 8 and 24 hours after surgery. This study found statistically significant decreased pain scores and opiate consumption among the Bupivacaine group for the first 24 hours after surgery (19). Studies have also been performed evaluating the use of intraperitoneal Bupivacaine vs Tramadol for management of postoperative pain during same day laparoscopic surgery. In a randomized trial of 90 patients assigned to intraperitoneal Bupivacaine (20 mL at 0.25%), IV tramadol hydrochloride (2 mg/kg), intraperitoneal saline (20 mL) or IV saline (2 mL) appreciated better analgesic outcomes among the Bupivacaine group (21).

Of the local anesthetic options available, Bupivacaine is known to have a longer duration of action compared to its counterparts (22). The maximum dose of Bupivacaine that should be administered is 2.0 mg/kg without epinephrine and 2.5 mg/kg with epinephrine (22). Therefore, the maximum allowable dose of Bupivacaine without epinephrine 0.25% should not exceed 56 mL in a 70 kg patient. While toxicity caused by local anesthesia can have CNS (nausea, vomiting, chills, pupil constriction, tinnitus, nervousness, dizziness, blurred vision, or tremors, followed by drowsiness, convulsions, unconsciousness, and possibly respiratory arrest as noted in the package insert) and CVS (depression of the myocardium, decreased cardiac output, heartblock, hypotension, bradycardia, ventricular arrhythmias, including ventricular tachycardia and ventricular fibrillation, and cardiac arrest as noted in the package insert when high doses or unintentional intravascular injection is administered) manifestations, these formulations have relatively wide safety margins and toxicity only occurs when these thresholds are exceeded (22, 23). One systemic review set out to evaluate the safety profile and systemic levels of local anesthesia following intraperitoneal administration (23). In this review, 415 patients were included, 11 (2.7%) were found to have systemic levels close to or above threshold and no cases of clinical toxicity were observed (23).

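### Surgical time and intraoperative complications are post-randomisation variables, but the plan calls them baseline, uses them to check randomisation and makes them eligible for adjustment

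*Combined protocol and SAP*

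**What the plan says.** Section 12.0 (Statistical Methods) names six baseline characteristics: surgical procedure, then "age, BMI, menopausal status, surgical time, and intraoperative complications". The complication variable is a single yes/no item for any complication, with no cause and no time window. The plan then states: "Baseline characteristics will be compared between the two study arms to verify randomization achieved balanced groups", and "Any characteristics that significantly differ will be considered in subsequent analyses". The primary model depends on the outcome of that check: "Assuming baseline characteristics are balanced between the two study arms, we will use a linear mixed model fit to all timepoints", with terms for surgery technique, treatment, time and time by treatment.

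Section 7.0 has the lavage given during the operation, at the point where peritoneal access is about to end, and "the solution will be left in the abdomen upon completion of the procedure". Section 5.0 lists the same two intraoperative variables simply as covariates to be collected, without calling them baseline.

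**The concern.** A comparison of arms can test randomisation only on variables fixed before allocation. Surgical time and intraoperative complications are not fixed until the operation ends, so a difference in them says nothing certain about the allocation process.

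The more serious matter is the route into the primary analysis. A variable that treatment can influence should not be a covariate in the model that estimates the treatment effect, because the adjustment removes any part of the effect that passes through it. It can also open a path through unmeasured causes shared with pain. For complications, a rule triggered by a significant difference is most likely to fire when the drug has in fact changed the rate, which is the one setting where adjusting does damage.

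The rule is also data-driven. It gives no significance level, no test, no model form, and no statement of whether the adjusted model would be primary or a sensitivity analysis.

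**Working it through.** **The plan's own figure.** Section 12.0 gives a difference of 1.3 and an SD of 2.14, so 1.3/2.14 = 0.607, used as 0.60. A two-sided two-sample t-test at 0.05 with 80% power needs 44.6, hence 45 per arm and N = 90 (power 80.4%). This reproduces. The point uses only the 45 per arm and the 1.3-point target.

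**Timing.** The moment of randomisation is not stated. Allocation must exist before the study solution is instilled (section 7.0), and the operation ends after that. Both variables are therefore completed after randomisation. This is an inference from the sequence of events, but a necessary one.

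**How often chance alone would trigger the rule.** Assume a 0.05 level and independent tests; the plan states neither.
- Two intraoperative variables: 1 − 0.95² = 9.75%.
- Five variables, leaving out the stratification factor: 1 − 0.95⁵ = 22.6%.
- These are nominal. With a 5% complication rate in both arms and 45 per arm, Fisher's test rejects in only 0.57% of trials, so the two-variable figure falls to 1 − 0.95 × 0.9943 = 5.5%.

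A chance trigger is a pre-specification problem. It does not bias the average estimate.

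**Size of the shift if the drug does affect complications.** In a linear model, the unadjusted effect equals the adjusted effect plus (NRS points per complication) × (difference in complication proportions). Assumptions, none of them in the documents: 5% on saline, 15% on bupivacaine, +1.5 NRS per complication, a 0.05 trigger, and adjustment whenever it fires. Summing over all pairs of binomial counts with 45 per arm:

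| Trigger test | Rule fires | Mean shift when it fires | Average shift over all trials | Share of 1.3 |
|---|---|---|---|---|
| Fisher | 23% | 0.27 | 0.06 | 5% |
| Uncorrected chi-square | 39% | 0.24 | 0.09 | 7% |

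The shift favours bupivacaine, because adjusting removes the extra pain that its complications would cause.

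**Range under other assumptions.** Simulation with 45 per arm, 3,000 runs per setting, a true total effect of −1.3, +1.0 NRS per complication and a Fisher trigger. Where a range is shown, the first figure has no unmeasured cause shared by complications and pain, and the second has one.

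| Complication rate, saline vs bupivacaine | Estimate under the rule | Estimate if always adjusted |
|---|---|---|
| 10% vs 10% | −1.30 | −1.30 |
| 10% vs 20% | −1.33 to −1.38 | −1.41 to −1.49 |
| 5% vs 25% | −1.47 to −1.62 | −1.49 to −1.68 |

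The shift is zero when the drug leaves the complication rate alone, and grows with the assumed drug effect.

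**The case against.** The best defence is that treatment has little opportunity to influence either variable. Instillation comes late, so most of the operation, and most chances for a complication, precede exposure. Both arms receive a 30 mL lavage under double blinding, and the documents give no route by which allocation would change surgical time. This stands: for surgical time the fault is the label and its use as a check on randomisation, not bias.

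A reader might infer from section 1.0, which lists "hypotension, bradycardia, ventricular arrhythmias" among bupivacaine effects, that the study drug is expected to cause intraoperative complications. The documents do not support that. The same sentence ties the cardiovascular effects to high doses or unintended intravascular injection and says toxicity arises only when dose thresholds are exceeded. The review it cites found no clinical toxicity in 415 patients. What remains is a possibility: 11 of those patients (2.7%) had levels close to or above threshold, and the yes/no item cannot separate events before instillation from events after it.

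A reader might also take the rule as automatic adjustment and quote a shift of 0.10 × 1.5 = 0.15 points, 12% of 1.3. The plan says only that differing characteristics will be considered, and only after a significant difference. The 0.15 figure would need adjustment in every trial. The fair criticism is that the wording leaves the decision open.

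Finally, it might seem that a drug-related safety difference would be hidden as chance imbalance. That is not established. Complications are to be tabulated by arm, section 9.0 covers reportable events, and section 10.0 has the monitoring board review adverse event data. It is true, though, that section 12.0 plans no safety comparison and would present any such difference under a baseline heading.

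**Conclusion.** The point holds in limited form. Two variables completed after randomisation are labelled baseline, used to verify randomisation, and made eligible for the primary model through an unspecified significance rule. That is unsound as written, whatever the drug does.

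Bias in the 4-hour effect is conditional. It arises only through complications, and only if bupivacaine changes their rate, which the documents leave possible but present as unlikely. Under the assumed 5% versus 15% and +1.5 NRS, the average shift is about 0.06 to 0.09 points in favour of bupivacaine; without a drug effect on complications it is zero. The event rates, the NRS effect, the 0.05 trigger and adjustment at every trigger are all assumptions. The case for change rests on the clear misclassification and the low cost of correcting it, not on a large expected bias.

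**What to change.** - Take surgical time and intraoperative complications out of the baseline balance check and out of the rule that brings differing characteristics into later analyses.
- Report both by arm as operative, post-randomisation data, with complications alongside safety.
- Replace the significance-triggered rule with covariates fixed in advance: surgery technique, plus any chosen from the pre-surgery variables already collected (age, BMI, menopausal status). State the primary model without the condition that baseline characteristics prove balanced.
- Label any model that adjusts for intraoperative variables as a sensitivity analysis.

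The cost is a wording change in section 12.0. No new data are needed and N = 90 is unchanged.
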